Primary outcome measures: (1) Proximal effects of CBT and ACT messages in the JITAI group: decreases over 20-minute intervals in craving and negative mood, with increases in self-efficacy; (2) strategy-situation fit in the JITAI group; (3) group differences in distal effects of treatment (week 11 versus week 2) in terms of self-efficacy and coping flexibility.

Secondary outcome measures: (1) Trait predictors of differential responses to CBT and ACT, in the JITAI group; (2) group differences in frequency of opioid-positive urine over time; (3) time courses of responsiveness to ACT vs. CBT, in the JITAI group; (4) whether the intervention types that benefit participants most when “pushed” by the app are the same ones participants choose when subsequently given the opportunity to “pull” interventions.

B. Table of Contents

A. Précis.....	2
B. Table of Contents.....	4
C. Background.....	5
1. From mobile assessment to mobile treatment: a microrandomization approach	5
2. Momentary interventions to be tested in the first arm of this protocol.....	7
3. Two ways to deliver a momentary intervention: push versus pull.....	9
4. Rationale for a multiple-arm protocol.....	10
D. Study objectives	10
E. Study design and methods	11
1. Overview of arm 1.....	11
2. Arm 1, Phase 1: Formative interviews.....	12
3. Arm 1, Phase 2: Clinical trial with microrandomization.....	12
F. Inclusion and exclusion criteria	24
1. Inclusion criteria.....	24
2. Exclusion criteria.....	24
G. Clinical and laboratory methods	25
H. Collection and storage of human specimens or data.....	30
I. Statistical analysis.....	31
1. Outcome measures.....	31
2. Analysis of study outcomes	31
3. Criteria for statistical significance.....	34
J. Required sample size	35
K. Plans for enrollment at multiple sites.....	36
L. Human-subjects protection plan	36
1. Rationale for subject selection based on gender/ethnic/race categories at risk.....	37
2. Recruitment plan	37
3. Justification for exclusion of vulnerable populations	38
4. Evaluation of risks/discomforts and benefits ratio	39
5. Subject monitoring	43
6. Conflicts of interest.....	44
M. Protection of participants' privacy and confidentiality	45
N. Study agents/interventions.....	45
O. Plan for reporting unanticipated problems and adverse events.....	45
P. Data and safety monitoring	45
Q. Clinical monitoring plan.....	46
R. Data/records management	46
1. Quality assurance.....	46
2. Relationship to other protocols	47
3. Data-sharing description.....	47

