Participants in the formative-interview phase may reenroll for the randomized treatment phase. We want to give them access to the potential benefits of the intervention. When we analyze results, we will test whether the interviewed participants respond differently from newly enrolled participants, as might be expected from their having had input into the app design.

After signing informed consent, each participant will be randomly assigned to one of two groups: JITAI intervention or EMA only.

During the first two weeks of participation, each participant will have an in-person session for training appropriate to his or her study group. All participants will be shown how to use the smartphone to make entries. Participants randomized to the JITAI intervention will be introduced to some basic principles of CBT and ACT. We are forgoing extensive in-person training in the hope of demonstrating that our ambulatory intervention can be effective without that. Mindfulness and ACT, like CBT, can be learned through “unguided self-help” (that is, without in-person training) (Cavanagh et al., 2014). A mere 11 minutes of prerecorded audio instruction on mindfulness, delivered in a clinic, was superior to a relaxation control condition

in helping at-risk drinkers reduce their drinking over the next week (Kamboj et al., 2017). We will provide more support: during the initial in-person session, each participant will watch a video introduction to both CBT and ACT. The video will be approximately 20 minutes long, and will be recorded by a counselor who has experience delivering these kinds of interventions for addiction. We will use just one counselor to discuss both techniques to avoid any confounding by participant preference for one counselor over another.

Before and after the video, one of the investigators at our clinic will talk with the participant to address concerns and discuss any material that the participant found unclear. Investigators will also be available to answer participants' questions about CBT and ACT throughout their time in the study, either during clinic visits, or by phone or online.

The content of the video will be underscored and complemented by a series of lessons/exercises that participants will read at home on their smartphone, one per night, for the first 16 nights of the JITAI intervention. We describe the lessons/exercises (to be referred to as "Deep Dives") further down, after we describe the JITAI intervention.

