For participants in the JITAI group, the content will be as follows:

1. “Pre” Assessment

—“Are you available now?” (If not, allow postponement up to 60 minutes.)

Baseline assessment of mindfulness with 2 items from the CAMS-R (Feldman et al., 2007) as adapted for EMA by Moore and colleagues (2016).

—“I am able to focus on the present moment.” (VAS slider 0-100)

—“I am able to accept the thoughts and feelings I have.” (VAS slider 0-100)

Baseline assessment of negative mood with items from the PROMIS questionnaire (Bjorner et al., 2014) as adapted for EMA by Moore and colleagues (2016).

—“I feel depressed.” (VAS slider 0-100)

—“I feel anxious.” (VAS slider 0-100)

—“I feel angry.” (VAS slider 0-100)

—“I feel stressed.” (VAS slider 0-100)

Baseline assessment of boredom, cue exposure, and drug craving:

—“I feel bored.” (VAS slider 0-100)

—“People, places, or things’ are reminding me of drugs.” (VAS slider 0-100)

—“I am craving drugs.” (VAS slider 0-100; also indicate which drugs)

Baseline assessment of situation category:

—“The best description of my situation right now is...

at home

at work

out doing obligations

out socializing or enjoying myself

other”

Baseline assessment of place:

— The place where I am is pleasant and comfortable (not too hot/cold, noisy, ugly, dangerous, etc.). (VAS slider 0-100)

— “I have privacy right now (or could easily get privacy if I wanted).” (VAS slider 0-100)

— “I could easily be somewhere else right now if I wanted.” (VAS slider 0-100)

Baseline assessment of activity:

— “What I’m doing right now is enjoyable for me.” (VAS slider 0-100)

— “What I’m doing right now is important to me.” (VAS slider 0-100)

— “I could easily get out of what I’m doing right now.” (VAS slider 0-100)

Baseline assessment of general self-efficacy:

—“I feel in control of my *responses* to what’s happening right now.” (VAS slider 0-100)

Baseline assessment of recovery self-efficacy, using an item adapted from Kranzler et al. (2016):

—“I’m confident that I can stick to my treatment goals for the rest of today/tonight.” (VAS slider 0-100)

Use of drugs since the previous assessment:

- “I have used an opiate since the previous assessment.” (yes/no)
- “I have used cocaine since the previous assessment.” (yes/no)
- “I have used other drugs since the previous assessment.” (yes/no)

Note: This “pre” assessment will also be given to the EMA-only group four times a day. Everything that follows will be given only to the JITAI group.

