Evening “Deep Dives” into ACT and CBT. For each of the first 16 evenings, the app will display a more in-depth lesson/exercise for participants in the JITAI group. The display time will have been selected by the participant during the issuing of the smartphone. The participant can “snooze” the “Deep Dive” (reschedule it for later in the evening), but has to read/do it on the scheduled evening. The “Deep Dives” (shown in Appendix B), which should each take approximately 5-15 minutes, will underscore and complement the general teaching on the introductory video. The intention is to provide skill training and philosophical context that will increase the value of the brief daily ACT and CBT messages. “Deep Dives” will alternate nightly between ACT and CBT and will be presented in the same order for all participants. The presentation of lessons in standardized sequence is typical for mobile interventions that include instructional modules. By giving the Deep Dives in the same order for everyone, we can present them more coherently. We think of the 16-night Deep Dive period almost as a psychological analog of a buprenorphine-induction period: at the end of it, every participant will have been titrated up to our targeted “dosage” of concept teaching and skill teaching.

We drew the material for the CBT “Deep Dives” from publicly available sources (such as the NIDA online “toolbox”); we drew the material for the ACT “Deep Dives” from publicly available sources and from a workbook by [name] (Hayes & Smith, 2005).

We will encourage participants to read/do the “Deep Dives” as scheduled, and we will discharge participants who have not done all 16 within the first 21 nights. That is, we will permit (but not encourage) up to five missed nights, and when a night is missed, the “Deep Dives” will resume with the missed material, adding one night to the total length of presentation.

The “Pull” Period. Participants in the JITAI group who complete the 7-week push period will immediately continue to the 1-week pull period. The pull period will be a superimposition of pull upon of push: push messages and assessments will continue as before, mostly because we want to continue collecting full daily data on every participant. But participants will also be able to initiate (pull) the “Deep Dives” they have already read/done, or view messages as

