of days in each study phase, and thus in the general timeline of the study. Further, due to the lack of a medication dose ceiling in this protocol and the desire to maximize taper success and participant comfort, the study physician may: (1) hold the medication taper at a given dose, which may add up to 2 weeks to this phase; (2) alter the taper decrement by requesting a specified dose decrease (e.g., decrease buprenorphine by 2mg x 3 days) which will slow the rate of taper and may add up to 2 weeks to this phase; and (3) may prescribe medications for the symptomatic relief of withdrawal signs and symptoms. These medications may include but are not limited to: ibuprofen, acetaminophen, hydroxyzine, dicyclomine, magnesium hydroxide, loperamide, and trimethobenzamide. These clinically indicated steps may add up to 2 weeks to the medication taper, which would result in a maximum total of a 7-week taper. These decisions will be made by the study physician as medically indicated based on withdrawal signs and symptoms and cravings.

Compliance with EMA and JITAI

If an OBOT participant misses 4 appointments, he or she may be discharged with a 21-day taper. Given their shorter length of participation, TE participants can be discharged if they miss 3 visits.

Participants must complete entries for at least 82% of all random prompts. This will be assessed weekly. Participants will receive approximately 28 prompts per week. Missing five entries per week would correspond to a compliance rate of 82.1%. If a participant falls below the 82% completion rate one week, the participant will be reminded of the requirement; if the participant remains below 82% during the next week, the participant will be eligible to be discharged. In the JITAI group, each pair of “pre” and “post” assessments will be counted as part of the same entry; both have to be completed for the entry to be considered completed.

Each participant will have a brief weekly meeting with a study-team member to receive a small payment (discussed in Section S, Compensation) for compliance with EMA requirements, or to be warned that he or she needs to comply with EMA requirements.

Participants in the JITAI group must read/do all 16 “Deep Dive” lessons/exercises within the first 21 nights of the JITAI intervention. Failure to do so will result in discharge.

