Other aspects of strategy-situation fit to be tested will include the setting (e.g., home, work, obligations, recreation), the nature of the problem (e.g., craving, boredom, anger), and cue exposure ("People, places, or things' are reminding me of drugs"). We will also examine alternative ways of operationalizing the controllability of a situation, because we know of no standardized way of doing so. In particular, we will examine the escapability of a situation in conjunction with its desirability, incorporating items such as "The place where I am is pleasant and comfortable (not too hot/cold, noisy, ugly, dangerous, etc.," "What I'm doing right now is

enjoyable for me,” and “What I’m doing right now is important to me.” We do not have *a priori* hypotheses for these analyses, and we will state that clearly when we report them.

Hypothesis 3, distal: Main effect of intervention (the group randomized to JITAI will have better outcomes—e.g. less drug use, higher self-efficacy, a greater increase in flexibility of coping styles—than the EMA-only control group when assessed at week 11).

These analyses, unlike the preceding ones, will use data from both the JITAI group and the EMA control group.

For group differences in mindfulness (FIT-60), coping self-efficacy (DTCQ), and coping-style flexibility (COPE), we will use analyses of covariance (ANCOVAs); in each ANCOVA, the dependent variable will be the score on the relevant measure at week 11, the categorical predictor will be group (JITAI vs. EMA) and the covariate will be the score at week 2.

The analyses on those questionnaire responses can be done only for participants who reach week 11. However, we will also test for a group difference in opioid use (thrice-weekly urinalyses) across the duration of the study. This analysis will use a generalized linear mixed model, so missing data (whether from early dropout or missed visits) will result in appropriately adjusted standard errors.

For a more stringent assessment of drug-use outcome, we will also compare the proportion of participants in each group who “succeed” in treatment (by completing week 11 and testing opioid-negative that week). Cessation of opioid use is not the main outcome measure for this study; we are more interested in psychological changes that might plausibly lead to good long-term outcomes. Nonetheless, we will assess and report this measure of treatment response.

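### The week-11 questionnaire comparisons under Hypothesis 3 use completers only, although two adherence demands after randomization fall on the JITAI arm alone, and no missing-data analysis is specified for them

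*Combined protocol and SAP*

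**What the plan says.** The précis lists among the primary outcomes "group differences in distal effects of treatment (week 11 versus week 2) in terms of self-efficacy and coping flexibility". Section I.2 (Hypothesis 3) tests DTCQ, COPE and FIT-60 by ANCOVA: the week-11 score on group, adjusted for the week-2 score. FIT-60 belongs to this set but is not in the primary list. The section then states: "The analyses on those questionnaire responses can be done only for participants who reach week 11".

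On timing, Section E.3 says: "After signing informed consent, each participant will be randomly assigned to one of two groups: JITAI intervention or EMA only". Two demands after that point concern JITAI only:

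- **Deep Dives.** Section E.3: "we will discharge participants who have not done all 16 within the first 21 nights". Section G (Compliance with EMA and JITAI) repeats the requirement and adds: "Failure to do so will result in discharge".
- **Paired entries.** The 82% weekly completion rule in Section G applies to both arms. In JITAI, however, the pre and post assessments form one entry, and "both have to be completed for the entry to be considered completed". The EMA-only group gets the pre assessment alone; the note in Section E.3 reads: "Everything that follows will be given only to the JITAI group". After one low week and a reminder, "if the participant remains below 82% during the next week, the participant will be eligible to be discharged". That is eligibility, not automatic discharge.

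Section I.2 also plans a mixed model of the urine results and a comparison of treatment success, which requires completing week 11 with an opioid-negative test. Section E.3 ends by saying that most remaining outcomes will be summarised from EMA and urine records, without specifying a between-group analysis of EMA self-efficacy. Section P.iii has one dropout check, after the first 10 enrolled, that does not mention arm, and ends the study at the target number of completers. Section J allows 150 enrolled to reach 85 completers (50 JITAI, 35 EMA) under unequal randomization and states no ratio beyond those targets.

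**The concern.** Randomization makes the two groups comparable at consent. The ANCOVA compares those who remain about ten weeks later. If the JITAI-only demands remove less adherent people from one arm, and adherence is related to the week-11 score, the group difference reflects who was kept as well as what the intervention did. The week-2 score adjusts for baseline differences on that score. It does not remove selection arising in weeks 3 to 10.

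At stake is the between-group test on two primary distal outcomes. Hypotheses 1 and 2 are tested within JITAI and do not use this comparison.

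**Working it through.** **The plan's own figures.** Section J gives power .90 at d = .70 and .80 at d = .60 for 50 and 35 evaluable participants, two-tailed .05. A two-sample t calculation gives .881 and .768, close to the stated values after rounding. These figures describe completers. Expected loss is up to (150 − 85)/150 = 43.3%.

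**How unequal the paired-entry rule can be.** Reaching 82% takes 23 of about 28 weekly prompts. I assume independent prompts and 90% pre completion. The chance of passing in a week is P(Bin(28, .90) ≥ 23) = .945 for EMA-only. For JITAI the per-prompt probability is .90 × (post completion):

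| Post completed | Per-prompt probability | Weekly chance of passing |
|---|---|---|
| 98% | .882 | .896 |
| 95% | .855 | .788 |
| 90% | .810 | .554 |

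**Size of the shift.** The documents give neither dropout by arm nor any adherence-outcome correlation, so both are assumed. Let adherence u be standard normal, let completers be those with u above the a-th quantile (a = fraction lost), and let ρ be the correlation of u with the week-11 score after baseline adjustment. Then E[u | complete] = φ(z_a)/(1 − a), and with no true effect

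shift = ρ × (JITAI value − EMA value).

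Enrollment needed is 50/(1 − a_J) + 35/(1 − a_E), which must not exceed 150.

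| Loss EMA / JITAI | Enrolled | E[u], JITAI − EMA | Shift at ρ = .3 / .5 (adjusted SD) | Type I error |
|---|---|---|---|---|
| 35% / 45% | 144.8 | .7196 − .5698 = .1498 | .045 / .075 | .054 / .069 |
| 30% / 50% | 150.0 | .7979 − .4967 = .3012 | .090 / .151 | .071 / .116 |
| 45% / 40% | 147.0 | .6439 − .7196 = −.0757 | −.023 / −.038 | .051 / .052 |

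Type I errors come from 20,000 simulated ANCOVAs with 50 and 35 completers. The largest shift, in raw SD with a baseline-outcome correlation of .5, is .1506 × √.75 = .130, or .130/.60 = 22% of the smaller detectable d in Section J.

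Equal loss does not by itself clear the comparison. With 43.3% lost in both arms and the same ρ there is no shift. With ρ = .5 in JITAI and .3 in EMA the shift is .139 adjusted SD (.120 raw) and type I error .104.

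**What imputation does.** Setting: 100 and 50 randomized, 30%/50% loss, ρ = .5, 30 imputations by arm, raw SD, no true effect except in the last column.

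| Analysis | Shift | SE | Type I error | True d = .60: estimate / power |
|---|---|---|---|---|
| Completers only | .134 | .177 | .133 | .724 / .97 |
| Imputed from baseline only | .135 | .182 | .123 | not run |
| + adherence, error-free | .005 | .260 | .045 | .599 / .60 |
| + adherence, reliability .7 | .088 | .225 | .066 | .683 / .84 |

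The .84 rests on an inflated estimate. If dropout is only partly driven by adherence, the completers-only shift falls to .092 (type I error .086). Imputation with adherence then gives .000, SE .211 and power .79.

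**What retrieval does** (one third of non-completers, reliability .7, against about .13 for completers only). The remaining shift is about .01 if responders are a random subset, about .05 to .06 if response follows adherence strictly, and about .10 to .12 if it depends on the week-11 score.

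**The case against.** The plan states the completers-only limit openly, and it does analyse data from dropouts elsewhere. A reader might infer that it has no all-randomized analysis at all. That is not so: the urine mixed model uses data from people who leave early. A reader might also infer that unequal loss would stay hidden. That goes too far, because the success proportion needs a denominator in each group and would partly reveal it. These parts of the objection stand. Both analyses concern drug use, however, which Section I.2 says is not the main outcome, so neither repairs the questionnaire comparison. The EMA summary measures in Section E.3 could supply a self-efficacy comparison that includes early leavers, but none is specified.

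It is also fair that every magnitude input is assumed, and that many losses come from rules common to both arms (missed visits, lost phones, clinic rules). The 20-point case with dropout wholly driven by adherence is near the upper end of what the enrollment ceiling permits.

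Finally, imputation is no clear improvement as a replacement. It does nothing from baseline alone, corrects only partly when adherence is measured with error, and costs precision. This is why the planned ANCOVA should stay.

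**Conclusion.** The concern holds for the questionnaire ANCOVAs. Retention into that analysis set depends on rules that differ by arm, and the plan specifies no missing-data analysis for DTCQ, COPE or FIT-60. Two of these three carry primary outcomes.

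Under the assumptions above, a 10-point gap shifts the result by 0.045 to 0.075 adjusted SD with type I error about .05 to .07, and a 20-point gap by 0.09 to 0.15 with about .07 to .12. Shifts are smaller if adherence only partly drives dropout, and slightly negative if controls leave more often.

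A reader might infer that the comparison is biased in favour of JITAI. The documents do not support that: they give no loss by arm and no link between adherence and outcome, and completer ANCOVA is unbiased if missingness depends only on arm and week-2 score. What they support is that bias of unknown size and sign is possible and that no planned questionnaire analysis would assess it. This should be fixed, but it does not invalidate the trial. Confidence is medium.

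**What to change.** 1. Keep the completers ANCOVA. Prespecify beside it an analysis of all randomized participants by assigned group, with multiple imputation done separately by arm from baseline scores, urine results, pre EMA answers and recorded adherence (pre completion and attendance in both arms; post and Deep Dive completion in JITAI). State the missing-at-random assumption, add a delta-shift sensitivity analysis, and draw the Hypothesis 3 conclusion in light of both analyses.
2. Report numbers randomized, retention, and discharge by arm and reason.
3. Where consent and the IRB permit, invite discharged participants to complete the week-11 questionnaires. State that this removes most of the bias only if responders are close to a random subset of those lost.

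Items 1 and 2 need plan wording and analysis time on data already collected. The price is a wider standard error (.225 to .260 against .177 in the worst case above). A person discharged over Deep Dives also leaves only about three weeks of EMA, so imputing week 11 is extrapolation. The all-randomized effect may be diluted as well.

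Item 3 needs IRB and consent changes, contact effort, and $40 per questionnaire set (Section S): 22 × $40 = $880 for a third of the 65 expected losses, and at most 65 × $40 = $2,600. For participants treated elsewhere, visit payments run up to $25 per week: 33 × $25 = $825 if half of the 65 are in that group and each comes for one week.

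The discharge rules are for the sponsor. The Deep Dive discharge rule in Sections E.3 and G is not named in the termination lists at the end of Section G and in Section L.5.B; these passages must be reconciled.
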